## **7.2 Phase II Arm**

The **Phase IIa Arm** can commence providing that a meaningful clinical response (partial or complete tumour response as determined by RECIST criteria) has occurred in some patients in the Phase Ib Arm. Up to a maximum of 12 patients can be recruited of similar tumour type and disease status as the Phase Ib patients showing the clinical response and form the basis of 2 new patient cohorts.

## 8 STUDY PARTICIPANTS

### 8.1 STUDY POPULATION

Patients with refractory solid tumors that have failed standard treatment options.

### 8.2 INCLUSION CRITERIA

Patients must fulfill all of the following inclusion criteria to be eligible to enroll into the study:

1. Provision of informed consent.
2. Male or female  $\geq 18$  years of age.
3. Histologic or cytologic confirmed locally advanced or metastatic cancer that has no standard therapeutic alternatives.
4. At least 1 measurable lesion by CT/MRI scan.
5. ECOG Performance status 0-1 (Appendix A).
6. A minimum life expectancy of 12 weeks.
7. Adequate bone marrow, hepatic and renal function as evidenced by:
  - Absolute neutrophil count (ANC)  $> 1.5 \times 10^9/L$
  - Platelet count  $> 100 \times 10^9/L$
  - Hemoglobin  $> 9.0$  g/dL
  - Serum bilirubin  $< 1.5 \times$  ULN
  - AST/ALT (SGOT/SGPT)  $< 2.5 \times$  ULN for the reference laboratory or  $< 5 \times$  ULN in the presence of liver metastases
  - Serum creatinine  $< 1.5 \times$  ULN
8. Female patients who are known to be capable of conception should have a negative serum pregnancy test (beta-human chorionic gonadotropin ( $\beta$ -hCG)) within 1 week of starting the study.
9. All potentially fertile patients will agree to use an effective form of contraception during the study and for 90 days following the last dose of NOX66 (an effective form of contraception is defined as an oral contraceptive or a double barrier method).
10. At least 4 weeks must have elapsed prior to commencement of NOX66 treatment since prior chemotherapy, investigational drug or biologic therapy and any toxicity associated with these treatments has recovered to  $\leq$  NCI-CTCAE Grade 1.

11. At least 21 days must have elapsed prior to Day 1 Cycle 1 since radiotherapy (limited palliative radiation is allowed > 2 weeks), immunotherapy or following major surgery and any surgical incision should be completely healed.

### **8.3 EXCLUSION CRITERIA**

Patients who have any of the following exclusion criteria are not eligible to participate in the study:

1. Patients who are pregnant or breastfeeding.
2. Tumor involvement of the Central Nervous System (CNS):
  - Patients with treated and stable CNS metastases may be eligible to participate after discussion and approval from the Medical Monitor.
3. Uncontrolled infection or systemic disease.
4. Clinically significant cardiac disease not well controlled with medication (e.g. congestive heart failure, symptomatic coronary artery disease, angina, and cardiac arrhythmias) or myocardial infarction within the last 12 months.
5. Patients with QTc of > 470 msec on screening ECG. (If a patient has QTc interval >470 msec on screening ECG, the screening ECG may be repeated twice (at least 24 hours apart). The average QTc from the 3 screening ECGs must be <470 msec in order for the patient to be eligible for the study.
6. Any major surgery, radiotherapy, or immunotherapy within the last 21 days (limited palliative radiation is allowed > 2 weeks).
7. Chemotherapy regimens with delayed toxicity within the last 4 weeks. Chemotherapy regimens given continuously or on a weekly basis with limited potential or delayed toxicity within the last 2 weeks.
8. Any situation where the use of suppository therapy is contra-indicated or impractical (eg. chronic diarrhea, colostomy, ulcerative colitis).
9. No concurrent systemic chemotherapy or biologic therapy is allowed.
10. Known human immunodeficiency virus (HIV) or Hepatitis B or C (active, previously treated or both).
11. History of solid organ transplantation.
12. Psychiatric disorder or social or geographic situation that would preclude study participation.

13. Known unsuitability for treatment with carboplatin including renal disease where there is impaired glomerular filtration rate (GFR).

#### **8.4 STUDY WITHDRAWAL**

It is planned that all enrolled patients will complete 1 treatment cycle at their assigned dose level. The patient can continue on idronoxil treatment at their allocated dose level weekly after Cycle 1 until demonstrated progressive disease according to Investigator's judgement, or a study withdrawal criterion is met.

Withdrawal criteria, other than progressive disease, can be defined as one or more of the following:

- an inter-concurrent illness that prevents further administration of NOX66;
- a DLT as defined in Section 10.1.4;
- an adverse event related to idronoxil that is intolerable;
- the patient withdraws consent;
- the patient dies;
- general or specific changes in the patient's condition render the patient unacceptable for further treatment in the judgment of the Investigator. In all cases, the reason for withdrawal must be recorded in the CRF and in the patient's medical records. The patient must be followed to establish whether the reason was an adverse event causally related to idronoxil therapy, and, if so, this must be reported in accordance with the procedures in Section 14.2.

#### **8.5 PATIENT REPLACEMENT**

Patients who cannot be evaluated as part of the efficacy analysis may be replaced in the study up to total of 16 evaluable patients.

Replacement will occur at end of all safety cohort assessments and patient may be enrolled at the highest tolerated dose level, commencing with treatment cycle 1 of Phase 1b.

## 9 STUDY MATERIALS

### 9.1 INVESTIGATIONAL STUDY PRODUCT

#### 9.1.1 Description and Formulation

The drug substance, idronoxil, is manufactured by chemical synthesis and is produced as a single monomer. Idronoxil is manufactured to c-GMP (< 99% purity) specifications.

#### Nomenclature

Codename:	Idronoxil
Chemical Name:	2H-1-Benzopyran-7-0,1,3-(4-hydroxyphenyl)
Other names:	Dehydroequisol
Empirical Formula:	C 15 H 12 O 3
Molecular Weight:	240.26 g/mol

NOX66 is idronoxil in a suppository dosage form for rectal delivery. The drug substance, idronoxil, is formulated in standard (commercial) fatty acid base (MBK®) to yield suppositories with an approximate weight of 2.2 gm and containing 400 mg drug substance. MBK® is a common suppository base for a wide range of marketed drugs and the methods of manufacture, moulding, lubrication and packaging are standard.

#### 9.1.2 Presentation, Storage and Handling

Presentation: NOX66 is presented as a solid dosage form suppository for rectal delivery.

NOX66 suppository product will be provided directly by Noxopharm Ltd, the Sponsor.

Storage and Handling: Boxes of NOX66 suppository should be stored at the study center in a secure area with limited access at 2-8°C (refrigerate), and protected from light. Any breach of investigational product storage conditions should be notified to the Sponsor on detection, and the study drug should be quarantined until the Sponsor authorizes usage or otherwise.

NOX66 suppository is not expected to pose any significant safety risks to the Investigational staff under normal conditions of storage and distribution. Idronoxil has the lowest grade (Grade 4) of hazard classification (according to Regulation (EC) No. 1272/2008 [EU-GHS/CLP]) with an acute oral toxicity of between 300 to >2000 mg/kg body weight. The product also is contained within air-tight plastic moulding.

### 9.1.3 Labelling

NOX66 suppository is presented in plastic sleeves in boxes. Each box contains 15 suppositories intended to provide 14 single doses, plus 1 spare dose.

Each box will be labelled with:

- the name of the Sponsor and address;
- the study protocol number;
- pharmaceutical dosage form, quantity of dosage units;
- name and strength of the product;
- the batch/lot number of the contents;
- period of use (expiry date or re-test date as applicable) in month/year
- Caution Statement: "Caution: Clinical Trial Use Only; Keep out of reach of children."
- storage instructions.
- PI name
- Patient ID

Each suppository will be labelled with:

- the name of Sponsor;
- the study protocol number;
- pharmaceutical dosage form, quantity of dosage units;
- name and strength of the product;
- the batch/lot number of the contents.

Boxes (plus any remaining contents) are to be accounted for.

### 9.1.4 Procurement and Distribution

NOX66 suppository study product will be provided directly by Noxopharm Ltd, the Sponsor.

Patients are to be given the requisite number of boxes of suppositories on Day 1 of the Treatment Cycle. Patients to return previously dispensed boxes at following visit for in-clinic administration and accountability.

The number of boxes of study product (NOX66) to be dispensed will vary with the NOX66 Treatment Regimen as shown in Table 1.

**Table 1. Number of Boxes of NOX66 to be Dispensed per Treatment Regimen**

Idronoxil cohort	Run-In Arm No. of boxes	Combination Arm No. of boxes
Cohort 1	1	1 per 2 cycles
Cohort 2	2	1 per cycle

## 9.2 INVESTIGATIONAL PRODUCT ADMINISTRATION

NOX66 suppository will be self-administered rectally either once or twice daily.

Patients will be provided with 'Instructions for the Use of a Suppository' for reference.

## 9.3 DURATION OF STUDY TREATMENT

Patients can continue to receive combination therapy of idronoxil and carboplatin at their allocated dose level for:

- up to 6 (six) 28-day treatment cycles OR
- until demonstrated radiologic and/or clinically assessed progressive disease OR
- until another withdrawal criterion is met (See Section 7.4).

## 9.4 TREATMENT DOSE MODIFICATIONS

There will be no dose modification of idronoxil on the basis of body weight except where the patient exceeds 100 kg body weight in which case the dose of idronoxil may be increased (up to double) at the discretion of the investigator.

If a patient experiences a  $\geq$  Grade 3 adverse event assessed as causally associated with idronoxil during the Run-In phase, the patient should be withdrawn from the study. If a patient experiences a  $\geq$  Grade 3 adverse event assessed as causally associated with idronoxil during the Combination Arm, the patient may continue on idronoxil treatment at their assigned dose provided:

- 1) the adverse event has resolved to no more than Grade 2 by the time of commencement of the next Treatment Cycle;
- 2) a treatment break of  $> 2$  weeks due to an unresolved adverse event will require discontinuation of study treatment.

## 9.5 ACCOUNTABILITY FOR CLINICAL SUPPLIES

The Principal Investigator will be responsible for the dispensing, inventory, and accountability of all clinical supplies, exercising accepted medical and pharmaceutical practices. An accurate and timely accountability record log of the disposition of all clinical supplies must be maintained. The supplies and inventory record must be made available for inspection by the Sponsor or the designated Sponsor's representative upon request. All used medication packaging and unused medication will be collected and retained until completion or termination of the study. Once all drug accountability has been performed the Investigator will destroy NOX66 suppositories as per Site Pharmacy SOPs and/or return all remaining clinical supplies to the Sponsor who will destroy the study drug on the site's behalf. Under no circumstances will the Principal Investigator allow NOX66 suppositories to be used other than as directed by this protocol.

## 9.6 CONCOMITANT MEDICATION

Patients are permitted a wide range of medications for general health, although this is to be confirmed with the Sponsor prior to enrolment into the Study.

Patients are permitted certain medications specifically related to their metastatic disease, but this again is to be confirmed with the Sponsor medical monitor prior to enrolment in the Study.

Patients are not permitted any other experimental drugs treatments.

Supportive care measures and symptomatic treatment for symptom control or drug-related toxicity are permitted including analgesics, etc. Erythropoiesis-Stimulating Agents (ESAs) are permitted but other hematopoietic growth factors are not. Although prophylactic anti-emetics and anti-diarrhoeals (eg. loperamide) are not permitted, they will be allowed if the patient experiences nausea, vomiting or diarrhoea.

Patients will be medically monitored so that any adverse events will be identified promptly and treated appropriately

Details regarding the name, indication, route of administration, dose, and frequency of all medications taken within 14 days prior to study drug administration will be recorded in the CRF at the Screening Visit and Day 1. Details regarding the name, indication, route of administration, dose, and frequency of all medications taken during the study will be recorded in the CRF at each patient visit. "All medications" should include prescription, over-the-counter (OTC) medications, dietary/nutritional supplements, and herbal products.

## 10 STUDY PROCEDURES AND VISITS SCHEDULE

The following section contains a detailed description of all study visits and procedures.

### 10.1 STUDY ARMS

#### 10.1.1 Phase Ia (Run-in) Arm

Sixteen (16) patients will be enrolled; 8 patients to be allocated to each of two Cohorts and administered idronoxil (NOX66 suppository) using a 2-step inter-patient dose escalation. There is no intra-cohort dose escalation. Table 2 shows the dosing schedule in terms of NOX66 product and the equivalent dosage of idronoxil.

**Table 2. NOX66/Idronoxil Dose Level Schema**

Treatment Regimen/ Cohort	NOX66 Dosage	Daily Idronoxil Dosage
1	One suppository, once daily	400 mg
2	One suppository, twice daily (12-hourly)	800 mg

Patients remain on the same daily dosage of idronoxil throughout all arms of the Study.

Idronoxil will be administered over a 21-day Treatment Cycle comprising daily NOX66 administration for 14 consecutive days followed by 7 days of rest.

Once Cohort 1 has enrolled 4 patients, further recruitment to that cohort will be suspended until the fourth evaluable patient completes 1 Treatment Cycle (including the 7-day rest period) and at least 3 of the 4 patients have not experienced any toxicity > Grade 2. The remaining 4 patients in Cohort 1 may then be recruited and start treatment.

Cohort 2 patients may commence idronoxil treatment once all 8 Cohort 1 patients have completed 1 (21-day) Treatment Cycle and at least 6 of those patients have not experienced any toxicity > Grade 2.

Where MTD is deemed to have been reached, up to 6 additional patients may be recruited into the particular cohort in order to confirm the tolerability of the MTD. However, it is not expected that MTD will be reached in this study.

**Table 3. Dose escalation Decision Rules for Run-In Arm**

Number of patients with toxicity > Grade 2 (or DLT) at a given dose level during the Run-In Arm	Escalation decision rules
0 out of 4	Remaining 4 patients in that cohort to be enrolled and to receive that dose level.
2 out of 8	Remaining 6 patients in that cohort to complete the Run-In phase and proceed to the Combination phase. Next cohort of patients may commence at the higher dose level
1 out of 34	
 
• Enter at least 2 more patients at this dose level
 
• If no further patients experience toxicity > Grade 2, patients to complete the Run-In Arm and proceed to the Combination Arm. Next cohort of patients may commence at the higher dose level.
 
• If 1 or more of this group experience > Grade 2 toxicity (2 of 8 dosed at this group), then dose escalation is stopped and this dose declared the maximally administered dose. Two (2) to 3 additional patients will be entered at the prior lower dose level if only 3 patients were treated previously at that dose.
 

≥ 2 out of 4	Dose escalation will be stopped. This dose level will be declared the maximally administered dose. Two (2) to 3 additional patients will be entered at the prior lower dose level if only 3 patients were treated previously at that dose.
≤ 1 out of 6 additional patients at highest dose level below the maximally administered dose	This dose is the MTD and is generally the recommended dose to be used in Phase 2 clinical trials. At least 6 patients must be entered at this dose. Note – this is only applicable if DLTs are experienced in the study in order to determine the MTD.

In the event of toxicity > Grade 2 in any Cohort 1 patient, the idronoxil dosage will be halved by reducing the dosage to 1 NOX66 suppository every second day. If toxicity > Grade 2 persists, the patient will be removed from the Study.

In the event of toxicity > Grade 2 with Idronoxil in any Cohort 2 patient and where the Investigator is confident that the toxicity is related to Idronoxil, the patient will revert to the lower dosage form and will remain at that dosage level for the completion of the 14-day Run-In period of treatment and will stay on that dosage level in the Combination Arm of the study. If toxicity > Grade 2 persists, the patient will be removed from the Study.

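### At 2 affected patients of 8 in Cohort 1, the run-in rules both permit and forbid opening 800 mg

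*Protocol*

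**What the plan says.** Five places set counts for the step from Cohort 1 (400 mg) to Cohort 2 (800 mg).

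- **Protocol Section 7 and SAP 2.2** bar recruitment to Cohort 2 until at least 7 of 8 Cohort 1 patients have finished a run-in cycle without a DLT.
- **Protocol 10.1.1, text after Table 2** counts toxicity above Grade 2, whatever its cause. After the first four, the condition is that "at least 3 of the 4 patients have not experienced any toxicity" above Grade 2; then "The remaining 4 patients in Cohort 1 may then be recruited and start treatment". Next, "Cohort 2 patients may commence idronoxil treatment once all 8 Cohort 1 patients have completed 1 (21-day) Treatment Cycle", provided "at least 6 of those patients have not experienced any toxicity" above Grade 2.
- **Protocol Table 3, row for 2 out of 8**: "Remaining 6 patients in that cohort to complete the Run-In phase and proceed to the Combination phase", and the next cohort may start at the higher dose.
- **Protocol Table 3, row for one early event** (label printed as 1 out of 34, read here as 1 of 4): "Enter at least 2 more patients at this dose level". If these are unaffected, the next cohort may start. If one or more is affected, the row gives the count itself: "2 of 8 dosed at this group), then dose escalation is stopped and this dose declared the maximally administered dose".
- **Protocol 10.1.4** places the MTD below a dose at which 2 of the first 4, or at least 3 of 8, have a DLT. Its closing sentence stops escalation once 2 or more patients have a DLT.

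The Table 3 column header counts toxicity above "Grade 2 (or DLT) at a given dose level during the Run-In Arm", which puts two different events under one count.

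**The concern.** Tolerability, DLTs and the MTD make up the first primary objective, and these counts decide whether patients receive the higher dose. At 2 of 8 the protocol gives both a go and a stop. Whoever makes the decision can cite current text for either answer, and it would be made with the toxicity data already known.

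The oversight provisions do not settle it. Protocol 11.1 and 14.2 have the Medical Monitor review toxicities and control enrolment, and SAP Section 9 foresees periodic data review. None of them gives a threshold or says which rule prevails.

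**Working it through.** **No figure to reproduce.** Protocol 13.1 calls 8 patients per combination adequate without a calculation, and no operating characteristics are given for the escalation rules. The check is therefore a comparison of the texts, followed by exact binomial probabilities under assumed rates.

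**Step 1. The rules side by side.** Write 1+1 for one affected patient in each group of four, and 0+2 for none and then two. Affected means toxicity above Grade 2. Every DLT listed in 10.1.4 is read as Grade 3 or higher, so DLTs are a subset.

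| Rule | 1+1, at most one DLT | 1+1, both DLTs | 0+2, at most one DLT | 0+2, both DLTs |
|---|---|---|---|---|
| Section 7, SAP 2.2 | no bar | barred | no bar | barred |
| 10.1.1 text | permits | permits | permits | permits |
| Table 3, 2-of-8 row | permits* | permits* | permits | permits |
| Table 3, 1-of-4 row | stops | stops | not applicable | not applicable |
| 10.1.4, closing sentence | no stop | stops | no stop | stops |
| 10.1.4, MTD definition | not met | not met | not met | not met |

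*Unless this row is read as covering only 0+2.

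Columns 1, 2 and 4 each contain a permission and a stop. Column 3 does not. So 1+1 is contested whatever share of toxicities are DLTs, and 0+2 is contested only if both events are DLTs.

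**Step 2. How often this would arise.** Inputs:

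- t is the rate of toxicity above Grade 2. It is an assumption: 2%, 5%, 10% and 20%. The documents give none. Protocol 5.3 (fatigue at most Grade 2, in under 5%), 5.6 and 10.1.1 (MTD not expected) suggest a low value.
- q = 1 - t.
- d is the share of these toxicities that are DLTs, also an assumption.
- Enrolment is 4 and then 4, as in the 10.1.1 text, with independent patients.

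Formulas:

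- P(1+1) = (4tq^3)^2 = 16t^2q^6
- P(0+2) = q^4 × 6t^2q^2 = 6t^2q^6, of which a fraction d^2 is contested

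At t = 5%, q^6 = 0.7351. So P(1+1) = 16 × 0.0025 × 0.7351 = 0.0294, and P(0+2) = 6 × 0.0025 × 0.7351 = 0.0110.

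| t | P(1+1) | P(0+2) | Contested part of 0+2 if d = 0.5 (one quarter) |
|---|---|---|---|
| 2% | 0.0057 | 0.0021 | 0.0005 |
| 5% | 0.0294 | 0.0110 | 0.003 |
| 10% | 0.0850 | 0.0319 | 0.008 |
| 20% | 0.1678 | 0.0629 | 0.016 |

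**Step 3. Chance of opening 800 mg.**

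- 10.1.1 text alone (at most 1 of 4, then at most 2 of 8): q^8 + 8tq^7 + 22t^2q^6.
- Every existing gate together (also at most 1 DLT of 8, and not on 1+1): q^8 + 8tq^7 + 6t^2q^6(1 - d^2).

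| t | 10.1.1 alone | Every gate, d = 1 | Every gate, d = 0 |
|---|---|---|---|
| 2% | 0.9975 | 0.9897 | 0.9918 |
| 5% | 0.9832 | 0.9428 | 0.9538 |
| 10% | 0.9300 | 0.8131 | 0.8450 |
| 20% | 0.7340 | 0.5033 | 0.5662 |

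**The case against.** The strongest reply is that the permissions only say the next cohort may start, while the bars are mandatory. Read so that every bar prevails, the rules give one answer at 2 of 8: stop on 1+1, and stop if both events are DLTs. This is a sensible safe reading, and the interim rule under the fix follows it. But no text says that the bars prevail, and 10.1.4 would still stop escalation at 2 DLTs while not placing the MTD below that dose until 3 of 8.

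Four stronger criticisms might be inferred, and the documents do not support them.

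- *Table 3 flatly contradicts itself.* It can be read by path: the 2-of-8 row for 0+2, the 1-of-4 row for 1+1. The conflict on 1+1 is then between Table 3 and the 10.1.1 text, and it remains.
- *The DLT gate and the above-Grade-2 gate are incompatible.* They count different events: the DLT definition leaves out, for example, controlled nausea and non-haematological events not attributed to NOX66. Three or more of 8 could have toxicity above Grade 2 with at most one DLT. But Section 7 is only a bar, so meeting it does not order escalation, and both gates can be applied together. What stands is that the Table 3 header does not say which event it counts.
- *Adding at least 2 contradicts adding 4.* Four is at least two, the same Table 3 row speaks of 8 dosed, and 10.1.1 requires all 8 to complete a cycle. What stands is that Table 3, read alone, could open Cohort 2 after 6 patients.
- *No other stopping threshold exists.* Protocol 10.1.2 stops dose escalation at a second DLT within any treatment regimen of the combination arm. It does not settle the run-in rules, but a single rule must be squared with it.

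The expected low toxicity is also a fair point. It makes the conflict unlikely to arise, but escalation rules are written for the case where that expectation fails.

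**Conclusion.** The concern holds at 2 of 8. On 1+1, the 10.1.1 text permits 800 mg and Table 3 stops it. With two DLTs, Section 7, SAP 2.2 and the end of 10.1.4 stop escalation, the 10.1.1 text and the Table 3 2-of-8 row permit it, and the MTD definition waits for 3 of 8. This follows from the wording and needs no assumed rate. The Table 3 header and the number entered after 1 of 4 are ambiguities, not strict contradictions.

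The size does rest on assumed rates and on 4+4 enrolment. The 1+1 path has probability 0.6%, 3%, 9% and 17% at rates of 2%, 5%, 10% and 20%. A reader might add the 0+2 path (0.2%, 1%, 3% and 6%) and call every 2-of-8 outcome contested. That overstates it, because 0+2 is contested only when both events are DLTs. The likely frequency is low, but a decision to raise the dose within a primary objective should have one answer, and correcting the text is cheap.

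**What to change.** Replace the counts in Protocol Section 7, 10.1.1, Table 3 and 10.1.4, and in SAP 2.2, with one decision table. It should name the event or events counted, give one action for each count at 4 and at 8 patients, use the same threshold in the MTD definition, and state how it relates to the second-DLT stop in 10.1.2.

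Until the clinical team chooses the threshold, apply every existing gate:

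- Enter the second four, all of them, only if at most 1 of the first 4 has toxicity above Grade 2.
- Open 800 mg only after all 8 have completed a cycle, with at least 7 of 8 free of DLT and at least 6 of 8 free of toxicity above Grade 2, and not on the 1+1 path.

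The cost is a protocol amendment and one SAP sentence. The interim rule also opens 800 mg less often than the 10.1.1 text alone: 94-95% against 98% at a 5% rate, and 81-85% against 93% at 10%. The ranges run from all to none of the toxicities being DLTs. Stopping more often may mean more use of the expansion of up to 6 patients that 10.1.1 already allows once an MTD is declared.

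A separate point also needs one stated action: Protocol 9.4 withdraws a run-in patient with a related event of Grade 3 or higher, while 10.1.1 and the synopsis reduce the dose and continue.

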Primary Study Objective	
 
to determine the tolerability, adverse event profile, maximum tolerated dose (MTD), and dose-limiting toxicities (DLTs) of idronoxil in a suppository dosage form (NOX66) in patients with refractory solid tumours, both as a single agent and in combination with carboplatin
 
to determine if idronoxil in a suppository dosage form (NOX66) is able to combine with a standard dosage of carboplatin to produce a meaningful anti-cancer effect in solid tumours considered to be refractory to cytotoxic chemotherapy
 
to determine if idronoxil in a suppository dosage form (NOX66) is able to combine with dosage of carboplatin two-thirds of the standard dosage to produce a meaningful anti-cancer effect in solid tumours considered to be refractory to cytotoxic chemotherapy
 

Secondary Study Objectives	
 
to characterise some key pharmacokinetic features of idronoxil when administered rectally
 
to determine if various biomarkers of idronoxil biologic activity have any correlation to the efficacy or toxicity of idronoxil in combination with carboplatin.
 

Methodology	
The Study has 3 separate components - Phase Ia, Phase Ib and a potential Phase IIa component.
 
The Phase 1a component will comprise 21-day Run-In Arm of idronoxil monotherapy administered on a two-step dose-escalation basis. Patients to receive idronoxil treatment once or twice (12-hourly) daily for 1 Treatment Cycle only.
 
Cohort 1: 400 mg idronoxil daily.
 
Cohort 2: 800 mg idronoxil daily.
 
In each regimen, treatment is taken daily for 14 consecutive days followed by 7 days of rest, comprising a 21-day Treatment Cycle.
 
Any patient experiencing Dose-Limiting Toxicity (DLT) in Cohort 1 will have their dosage halved to 400 mg idronoxil every 2nd day.
 
Any patient experiencing DLT in Cohort 2 will revert to Cohort 1 treatment regimen.
 
The Phase Ib component will comprise idronoxil administered in combination with carboplatin up to 6 Treatment Cycles each of 28-days.
 
All patients completing the Run-In Arm without significant toxicity will be offered combination treatment with carboplatin. Patients will remain in the same Cohort

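### For an idronoxil-related Grade 3 or higher run-in event, Protocol 10.1.1 and the synopsis reduce the dose and continue, 9.4 withdraws the patient, and no text says which governs

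*Protocol*

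**What the plan says.** Four places in the protocol state what happens to a patient with severe toxicity in the Phase Ia run-in.

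- **Section 10.1.1, after Table 3.** For Cohort 1: "In the event of toxicity > Grade 2 in any Cohort 1 patient, the idronoxil dosage will be halved", meaning one suppository every second day. For Cohort 2, where toxicity exceeds Grade 2 "and where the Investigator is confident that the toxicity is related to Idronoxil", the rule is that "the patient will revert to the lower dosage form and will remain at that dosage level for the completion of the 14-day Run-In period", and the lower dose carries into the Combination Arm. In both cohorts removal follows only if toxicity above Grade 2 persists.
- **Synopsis, Methodology.** After a DLT, a Cohort 1 patient goes to alternate-day dosing. For Cohort 2: "Any patient experiencing DLT in Cohort 2 will revert to Cohort 1 treatment regimen".
- **Section 9.4.** For a Grade 3 or higher adverse event "causally associated with idronoxil during the Run-In phase, the patient should be withdrawn from the study". The same section lets a patient continue after such an event only in the Combination Arm, and on conditions.
- **Section 8.4.** The list of what withdrawal criteria can be includes "a DLT as defined in Section 10.1.4".

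Two other texts bear on who goes on to Phase Ib. Table 3's row for 2 of 8 patients with toxicity says: "Remaining 6 patients in that cohort to complete the Run-In phase and proceed to the Combination phase". The synopsis says: "All patients completing the Run-In Arm without significant toxicity will be offered combination treatment with carboplatin".

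**The concern.** Toxicity above Grade 2 and Grade 3 or higher are the same thing, so 10.1.1 and 9.4 address the same run-in events and prescribe opposite actions. A site cannot follow both. Section 16.3.1 defines any deviation as a protocol violation, so either choice departs from a written rule.

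The main stake is patient safety: whether a patient with a severe drug-related event stays on the drug. The second is who reaches Phase Ib. The SAP's efficacy population requires a completed combination cycle, so the choice also affects who is counted for response. The SAP (3.3) names four sites and plans no analysis by site, so differing practice between sites would not be separated in the summaries.

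**Working it through.** There is no stated figure to reproduce and no hypothesis test involved. The check sets the rules side by side and applies them to the same event.

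**The rules**

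| Place | Trigger | Action |
|---|---|---|
| 10.1.1, Cohort 1 | Toxicity above Grade 2; relatedness not mentioned | Halve dose; remove if it persists |
| 10.1.1, Cohort 2 | Toxicity above Grade 2, Investigator confident it is related | Drop to 400 mg; remove if it persists |
| Synopsis | DLT | Halve dose, or revert to Cohort 1 regimen |
| 9.4 | Grade 3 or higher, causally associated | Should be withdrawn |
| 8.4 | DLT | Listed withdrawal criterion |

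**Case 1: a related Grade 3 non-laboratory event that meets 10.1.4.** 10.1.1 and the synopsis reduce and continue; 9.4 withdraws; the criterion in 8.4 is met.

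**Case 2: a related Grade 3 event outside the DLT definition**, such as nausea controlled with supportive care or neutropenia lasting under 5 days. 10.1.1 reduces and 9.4 withdraws. The synopsis and the DLT criterion in 8.4 do not apply.

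**Does any text reconcile them?**

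- The persistence clause in 10.1.1 does not, because 9.4 acts at the first event.
- Section 9.4 contrasts the run-in with the Combination Arm, so its withdrawal rule is specific to the run-in.
- The discussion between Investigator, Medical Monitor and Sponsor in 10.1.2 covers Combination Arm DLTs only.
- Section 14.2 covers toxicity review and enrolment decisions.
- The Day 21 call in Table 5 confirms dose level and continuation but states no rule, and it follows the last run-in dose on Day 14.
- The SAP does not address dose reduction within a patient.

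**Illustrative size.** Assumptions: action from Day 8, reduction tolerated, and all six planned Phase Ib cycles completed with 7 dosing days each. Many refractory patients would stop earlier, so the totals under reduction are upper bounds for the planned course.

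Cohort 2:
- Withdraw: 7 × 800 = 5,600 mg, 0 combination cycles.
- Reduce: run-in 7 × 800 + 7 × 400 = 8,400 mg; Phase Ib 6 × 7 × 400 = 16,800 mg; total 25,200 mg, up to 6 cycles.
- Never reduced: 14 × 800 + 6 × 7 × 800 = 44,800 mg, so the reduced patient receives 25,200 / 44,800 = 56%.
- Varying the day of action: Day 2 gives 800 + 13 × 400 + 16,800 = 22,800 mg (51%); Day 14 gives 13 × 800 + 400 + 16,800 = 27,600 mg (62%).

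Cohort 1:
- Withdraw: 7 × 400 = 2,800 mg, 0 cycles.
- Reduce: run-in (7 + 4 doses on Days 8, 10, 12, 14) × 400 = 4,400 mg. Phase Ib at 3, 4 or 7 suppositories per cycle adds 7,200, 9,600 or 16,800 mg, for totals of 11,600, 14,000 or 21,200 mg. The range arises because the plan gives no Phase Ib dosing days for such a patient.
- Never reduced: 5,600 + 16,800 = 22,400 mg.

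**Patients affected.** At 2 of 8 with toxicity, 6 or 8 run-in patients go on to Phase Ib, depending on the rule followed. If reduction is kept and both are in Cohort 2, 2/8 = 25% of the column labelled 800 mg would be taking 400 mg in Phase Ib.

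**The case against.** The strongest reply is that the conflict comes down to one sentence in 9.4, worded as should, against two consistent texts, and that other provisions limit the harm. Much of this stands.

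- **Recovery check.** Section 10.1.2 starts combination only when residual toxicity is no worse than Grade 1 or the Investigator judges the patient recovered. A reader might infer that patients with unresolved Grade 3 toxicity go straight to carboplatin; the protocol does not allow that. The check also gives working meaning to the synopsis condition about significant toxicity. It does not decide whether the patient should still be on study, or on what run-in dose.
- **Section 8.4.** Its permissive wording makes it weaker support for withdrawal than 9.4.
- **Table 3.** The 2 of 8 row does not say that the other two patients are excluded. It is unclear rather than contradictory.
- **Replacement.** Section 8.5 allows non-evaluable patients to be replaced up to 16 evaluable, so the issue is more who enters Phase Ib than how many.

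Three stronger readings are tempting but not supported:

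- **That a reduced Cohort 1 patient has no workable Phase Ib schedule.** Dosing on Days 2, 4 and 6 misses Day 7, and Days 1, 3, 5 and 7 miss Day 2. Table 6 allows 1 day either side for each visit, so either pattern fits. What is missing is a statement of the dosing days.
- **That the sentence in 10.1.1 keeping patients on one daily dosage is a further conflict.** It is a default, and the reduction text is an explicit exception in the same section.
- **That the SAP fails to present data by idronoxil dosage.** It labels cohorts 400 mg and 800 mg and splits adverse events by carboplatin AUC, on an assigned-dose basis. Protocol 13.2 also plans listings of all collected data.

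**Conclusion.** The contradiction stands. For an idronoxil-related Grade 3 or higher run-in event, 10.1.1 and, where the event is a DLT, the synopsis keep the patient on a reduced dose, while 9.4 withdraws the patient at the first event. No precedence is given. It should be corrected because it concerns the handling of severe toxicity in individual patients and the change is cheap.

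The scope is limited. A reader might infer that dose finding is compromised, but DLT counts and the escalation decisions based on them rest on the first event and do not depend on what happens to the patient next. The analyses are descriptive, with 8 patients planned per cohort. An analysis consequence arises only if reduction is kept: adverse events starting after a reduction would be tabulated under the starting dose. Planned listings, and one adverse event table with subject identification, partly offset that.

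The milligram totals illustrate how far the two rules diverge; they are not expected exposures. They rest on the assumed day of action and full completion of six cycles. The text conflict does not depend on them.

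**What to change.** **Trigger.** Use one trigger in both cohorts: any toxicity above Grade 2 rated possible, likely or certain for idronoxil under Table 12, or any DLT under 10.1.4. Leave 10.1.4 unchanged. A DLT alone would be too narrow, because related Grade 3 events outside that definition would then have no stated run-in action. This trigger would end the Cohort 1 reduction for unrelated events that are not DLTs.

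**Action.** State one action and make the synopsis, 8.4, 9.4 and 10.1.1 agree. The choice belongs to the sponsor and investigators.

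- **(A) Reduce once, and withdraw if toxicity above Grade 2 persists or recurs.** Replace the run-in withdrawal sentence in 9.4, limit the DLT criterion in 8.4 to persistent or recurrent DLT, and say in Table 3's 2 of 8 row whether reduced patients may proceed to Phase Ib. State the Phase Ib dosing days for a Cohort 1 patient on alternate-day dosing. In the SAP, flag adverse events that start after a dose reduction.
- **(B) Withdraw at the first event.** Delete the reduction text in 10.1.1 and the synopsis.

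**Cost.** Text edits through a protocol amendment, with ethics committee notification and, under 16.4, documented approval if the change may increase risk. Option (A) adds one SAP flag derived from dosing records. Neither option needs extra patients or procedures.
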